### 6.2 Secondary Endpoint

The secondary endpoint for Aim 2b will be the frequency and phenotype of circulating B and T lymphocytes, which will be measured at roughly 3, 6, and 12 months for each subject. We specifically have an interest in the recovery of Tfh as they provide required help to B cells in the follicles of lymphoid tissues.

### 6.3 Statistical Methods

#### 6.3.1 Baseline Data

Baseline and demographic characteristics will be summarized by standard descriptive summaries. Categorical variables will be summarized by frequencies while continuous variables will be summarized by using mean, standard deviation, median, twenty-fifth and seventy-fifth percentiles, minimum and maximum.

#### 6.3.2 Analysis of Aim 1

Aim 1 (total number of unique infections identified within the first year after completing chemotherapy) will be reported as a rate per 1000 follow-up days. This rate will be reported for the entire cohort, by study site, and by demographics (e.g., age, race, gender). This outcome will also be reported within subsets of infection type (i.e., microbiologically documented infections and bacterial sinopulmonary infections) also reported as a rate per

---

1000 follow-up days for the entire cohort, by study site and by specific demographic variables. All infection rates will be reported as a post estimate with 95% confidence intervals. Patients will be censored at time of lost to follow-up or death.

Infection rates for enrolled patients will also be compared to those of controls matched on age and sex selected from the CHOP Pediatric Research Consortium (PeRC). Three healthy controls will be selected for each participant for a case to control ratio of 1:3. Control patient infection data will be obtained for the same follow-up time period as that of the matched case patient in order to match risk for infection from seasonal pathogens (e.g., if a case patient completed ALL therapy and enrolled in the study in January 2023, infection data for the matched controls would be collected from January 2023 through December 2023, the same follow-up period as that of the case patient). All control patients will be randomly selected, and control data will be collected when follow-up is complete for participants in the ALL cohort.

Infection rates will also be generated for patients who received blinatumomab as part of their chemotherapy regimen and those who did not receive blinatumomab.

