At the end of 2024, the Children's Oncology Group reported data from a randomized controlled trial revealing improved effectiveness of ALL chemotherapy regimens inclusive of the novel biological agent blinatumomab. The improved outcomes of patients receiving ALL chemotherapy inclusive of blinatumomab has led to immediate transition to this regimen as standard of care for most patients with ALL. While blinatumomab may have improved effectiveness for cure of cancer it may alter immune reconstitution trajectories in the survivorship period. Because most of this study cohort was enrolled prior to the institution of blinatumomab as standard of care, it is uniquely positioned to now enroll ALL survivors that have or will have received blinatumomab as part of their chemotherapy

---

regimen. Including blinatumomab recipients will provide exploratory data on potential differences in immune reconstitution between patients receiving this new standard of care relative to prior standard of care ALL chemotherapy regimens.

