## **2 STUDY OBJECTIVES**

### **2.1 Primary Objective (or Aim)**

Aim 1: To determine the overall infection incidence rate within the first year following completion of therapy for acute lymphoblastic leukemia and compare that rate with the rate of infections occurring in age- and sex-matched healthy control patients during the same time period.

- Sub-aim: To examine infection incidence in patients who received the monoclonal antibody blinatumomab as part of their ALL treatment protocol versus that of patients who did not receive blinatumomab.

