### **6.3.4 Control of Bias and Confounding**

For Aim 1, patients will be contacted once monthly for symptom reporting. Capture of the primary outcome will be dependent on completion of study visits, phone calls and complete data collection from the medical record. Accordingly, study procedural protocols will be implemented to ensure systematic approach for each enrolled subject. We will also develop a database that will inform a systematic approach to medical record review. This is a descriptive study and thus is not vulnerable to confounding.

To control for possible confounding in the comparison of infection incidence rates of ALL patients to those of healthy control patients, all healthy control patients will be matched to ALL cohort patients based on both age and sex, and controls will be assigned the same one-year “follow-up” period as those of their matched ALL cohort patients, to account for seasonal variation in infection rates as described above. Demographic data and vaccination histories

will be collected as outlined above for both ALL cohort patients and healthy controls to monitor for balance with respect to these important factors. Healthy control patients will be included only if they do not have pre-existing medical conditions that might put them at increased risk for infection to ensure assembly of a healthy cohort that most closely mirrors the general population of healthy children. Further, to reduce the risk of selection bias in the healthy control cohort, a waiver of consent and HIPAA authorization will be requested for these patients.

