#### 6.4 Sample Size and Power

This study aims to enroll 110 ALL cohort subjects across several centers for Aims 1 and 2. The complexity of specimen processing for Aim 2b will limit performance of these assays to approximately 40 of the overall 110 subjects.

For Aim 1, a cohort of 330 matched healthy control patients will be assembled for the purpose of comparison of infection incidence rates in healthy patients versus those who recently completed ALL therapy. Based on preliminary data collected on this study's cohort of ALL patients, the infection incidence rate in the first year after completion of chemotherapy is estimated to be 1.88 events per person-year. For this power calculation, we assume the rate of infection for the entire ALL cohort will mirror the currently estimated rate of 1.88 events per person-year, assume a two-sided type I error of 0.05, and range the values of overdispersion parameter from 1 to 3.

With 50 ALL patients and 150 matched healthy participants (1:3 match) and one year of follow up on each participant, the detectable effect size with at least 80% power is summarized in Table 1. For example, under the assumption of no overdispersion (overdispersion parameter=1), we will have 80.1% power to detect an IRR of 1.45, i.e., incidence rate of 1.88 for cancer cohort vs. 1.30 for healthy cohort. Under the conservative assumption of a larger overdispersion parameter of 3, we will have 80% power to detect an

IRR of 1.90, i.e., incidence rate of 1.88 for cancer cohort vs. 0.99

for healthy cohort. Although we do not have an accurate estimate of the event rate in the healthy cohort, an IRR in the range of 1.45 to 1.90 represents

a clinically meaningful effect size for which we will have sufficient power to detect.

**Table 1.** Power calculation Across Multiple Estimates of Baseline infection Event Rate, Detectable Incidence Rate Ratios, and Overdispersion Parameters

Infection event rate in the healthy cohort	IRR	Overdispersion parameter	Power
1.30	1.45	1	80.1%
1.19	1.58	1.5	81.0%
1.11	1.69	2	80.1%
1.04	1.81	2.5	81.2%
0.99	1.90	3	80.0%

The descriptive and comparative results from Aim 1 will provide important point estimates for infection in the first year post ALL chemotherapy that clinicians can use to manage family expectations for this recovery period.

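### The Aim 1 blinatumomab sub-aim is answered only by two crude infection rates, although receipt of the drug is strongly tied to calendar period

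*Combined protocol and SAP*

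**What the plan says.** Under the primary aim, section 2.1 lists a sub-aim on infection incidence in blinatumomab recipients "versus that of patients who did not receive blinatumomab". The Aim 1 analysis of it in section 6.3.2 is a single sentence: "Infection rates will also be generated for patients who received blinatumomab as part of their chemotherapy regimen and those who did not receive blinatumomab". The same section reports every infection rate with a 95% confidence interval. It gives no ratio, model, calendar stratification or caveat for this comparison.

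On timing, section 1.2 explains the sub-cohort this way: "Because most of this study cohort was enrolled prior to the institution of blinatumomab as standard of care", the study is now well placed to enroll recipients. It dates the trial report behind the change of practice to the end of 2024. Screening (section 4.1) goes back to patients finishing therapy from 1 December 2021. Section 3.1 puts the sub-cohort at 20-25 patients.

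For the comparison with healthy controls, sections 6.3.2 and 6.3.4 give each control the follow-up window of the matched patient, to deal with seasonal variation. Section 6.3.4 also says: "This is a descriptive study and thus is not vulnerable to confounding".

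**The concern.** The plan recognises that infection risk depends on when a child is followed, and it controls for this in ALL versus healthy controls. It does not do so for blinatumomab versus no blinatumomab, where timing and group are linked by the way the cohort was assembled. Non-recipients were mostly followed in earlier years, and recipients will mostly be followed later. If circulating infections differ between those years, the two crude rates will differ even if the drug has no effect, and the difference could go in either direction. A reader who sees two rates with two intervals under a comparative sub-aim will tend to read the gap as something about blinatumomab. Such a reading could shape the later studies that this cohort is meant to inform.

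**Working it through.** **Inputs from the documents.** The ALL infection rate "is estimated to be 1.88 events per person-year" (6.4). The plan will "range the values of overdispersion parameter from 1 to 3" (6.4). There are 110 evaluable ALL patients (3.2.2) and 20-25 recipients (3.1), which leaves 85-90 non-recipients. There are three controls per patient. Table 1 takes healthy rates from 1.30 to 0.99 per person-year.

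**Inputs assumed.** The background shift c between the earlier and later period, and the fraction f of non-recipients followed in the later period. Neither is in the documents, so ranges are shown.

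**1. The plan's own figure.** The plan gives no power or precision for the blinatumomab comparison. Table 1 covers only ALL versus healthy: "With 50 ALL patients and 150 matched healthy participants (1:3 match) and one year of follow up on each participant", and the authors "assume a two-sided type I error of 0.05". For its first row, the Wald formula with SE = √(1/(50×1.88) + 1/(150×1.30)) = 0.1256 and ln(1.88/1.30) = 0.369 gives z = 2.94 and power Φ(2.94 − 1.96) = 83.6%, against 80.1% stated. Simulation with a robust-SE Wald test gives 82.1, 82.0, 81.4, 81.0 and 79.7% for the five rows, against 80.1, 81.0, 80.1, 81.2 and 80.0%. All are within 2 points, so the rate model and inputs are usable here. Nothing in Table 1 is in dispute.

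**2. Crude ratio with no drug effect.** Recipients, all in the later period, have rate 1.88c. Non-recipients have rate 1.88 × [(1 − f) + fc]. The crude ratio is c / [(1 − f) + fc].

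| Shift c | f = 0 | f = 10% | f = 25% |
|---|---|---|---|
| 0.7 | 0.70 | 0.72 | 0.76 |
| 0.8 | 0.80 | 0.82 | 0.84 |
| 1.2 | 1.20 | 1.18 | 1.14 |
| 1.3 | 1.30 | 1.26 | 1.21 |
| 1.5 | 1.50 | 1.43 | 1.33 |

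For example, 1.3/(0.75 + 0.25×1.3) = 1.3/1.075 = 1.21, and 1.5/1.125 = 1.33. Overlap shrinks the bias but does not remove it.

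**3. Ratio of matched IRRs.** Let healthy controls have rate h and the same shift. Recipients against their controls give 1.88c/(hc) = 1.88/h. Non-recipients against theirs give 1.88[(1 − f) + fc] / (h[(1 − f) + fc]) = 1.88/h. The ratio is 1.00 for any c and f. This holds by construction, because the controls are assumed to share the shift.

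**4. Price in precision.** With overdispersion φ and n₁, n₂ patients, the crude log-ratio variance is φ(1/(1.88n₁) + 1/(1.88n₂)). The controls add φ(1/(3hn₁) + 1/(3hn₂)), which is the crude variance times 1.88/(3h). The SE is therefore multiplied by √(1 + 1.88/(3h)):

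- h = 1.30: √(1 + 1.88/3.90) = 1.217
- h = 0.99: √(1 + 1.88/2.97) = 1.278

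**5. What a reader would see.** Take 20 versus 90 patients, c = 1.3, f = 0, h = 1.30, φ = 1. The crude SE is √(1/(20×1.88×1.3) + 1/(90×1.88)) = √(0.02046 + 0.00591) = 0.162, so the crude ratio is 1.30 (95% CI 0.95 to 1.79). Adding 1/(60×1.30×1.3) + 1/(270×1.30) = 0.0127 gives SE 0.198, so the ratio of IRRs is 1.00 (0.68 to 1.47). At φ = 3 the intervals are 0.75 to 2.26 and 0.51 to 1.96.

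**The case against.** Several parts of the opposing case stand.

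- **No test is planned.** Section 6.3.2 treats the blinatumomab groups descriptively, much as it treats site, age, race and gender, and section 6.4 powers only ALL versus healthy. Section 1.2 calls the blinatumomab data exploratory, although that wording concerns immune reconstitution. A reader might infer a high false-positive rate for a drug effect. The documents do not support that, because there is no test whose error rate could be inflated.
- **Separation may be incomplete.** A reader might infer that the two groups sit in wholly different years. Section 1.2 says only that most of the cohort came earlier. It does not exclude early recipients, and section 3.3.1 does not bar later non-recipients.
- **The shift is assumed.** The documents contain no yearly infection rates.
- **The controls are an imperfect yardstick.** They all come from CHOP, wherever the matched patient was enrolled (Abstract, Setting/Participants), while patients come from seven centers. ALL patients are contacted monthly (6.3.4), whereas control data come from an automated record pull with chart abstraction as needed (7.1). The ratio of IRRs does not touch differences such as leukemia type or age at treatment.
- **Precision is poor.** With 20 recipients, the crude ratio detectable with 80% power is 1.53 at overdispersion 1 and 1.97 at 3. Widening the SE by 1.22 and 1.28 gives roughly exp(1.22 × ln 1.53) = 1.7 and exp(1.28 × ln 1.97) = 2.4.
- **The confounding sentence has a context.** It closes a paragraph on outcome capture, and the next paragraph deals with confounding in the healthy-control comparison. A reader might infer that the plan denies confounding altogether. It does not.

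These points limit the size and certainty of the concern but do not answer it. The sub-aim is explicitly comparative, and nothing in the plan addresses calendar period for it. A caveat alone would warn the reader without supplying a period-controlled estimate.

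**Conclusion.** The point holds as a gap in the analysis of an exploratory comparison. A comparative sub-aim is answered by two crude rates from groups that the protocol's own account ties strongly to calendar period, with no period control or caveat. Any background change would pass into the crude ratio in full under complete separation, and in large part under moderate overlap. The figures 1.3 and 1.5 (or 1.21 and 1.33 with 25% of non-recipients in the later period) rest on an assumed shift, no drug effect and all recipients being in the later period. They illustrate the bias and do not forecast it. The harm is misreading of two descriptive rates. The main ALL versus healthy comparison already uses same-window controls and is not affected by this point.

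**What to change.** In section 6.3.2, keep the crude rate for each blinatumomab group and label it descriptive. Add, as the period-controlled comparison, the ratio of two matched IRRs: recipients versus their own same-window controls, divided by non-recipients versus theirs. It should carry a 95% CI and be labelled exploratory. It can be fitted as the interaction between cohort (ALL or control) and blinatumomab status of the matched set, in one rate model on all 440 subjects, with a variance that allows for overdispersion.

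State its limits beside it:

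- Controls come from CHOP only, so it removes only period changes shared across sites.
- It assumes that ascertainment of infections in patients relative to controls is stable over time.
- It does not remove differences between the groups such as leukemia type.
- Its log-scale SE is about 22-28% wider than that of the crude ratio.

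In section 6.3.4, restrict the statement on confounding to the single-cohort descriptive rates.

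The cost is a few sentences of SAP text and one model term. No new patients, visits or data are needed, because three same-window controls per patient are already planned. The wording should be fixed before the control data are collected, so that the choice of comparison is not made after seeing the rates.

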### **6.3.3 Analysis of Aim 2**

The total IgG levels and specific seroprevalence proportions for each of the three pathogens (measles, pneumococcus, and varicella) of interest will be determined for the entire cohort and by demographics (e.g. age, race, gender) at each study follow-up time point (i.e. about 3, 6 and 12 months). Additionally, seroprevalence at each time point will be described for subjects that had and had not completed their primary vaccine series before starting ALL chemotherapy, as well as for those who received blinatumomab as part of their chemotherapy regimen and those who did not.

T and B lymphocyte subsets will be measured for a subset of the 110 enrolled subjects. These measurements will be reported for each subject at approximately 3, 6, and 12 months. The trajectory of these measurements will be displayed graphically across the three timepoints of interest to assess relative recovery of lymphocyte quantities after completion of ALL chemotherapy.

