### 1.2 Relevant Literature and Data

Advancements in therapy have led to significant improvement in outcomes for children diagnosed with ALL, with overall survival rates now exceeding 90%. Although this therapy is lifesaving, its use is well known to impact vaccine- and infection-acquired immunity. As a result, infection remains a significant cause of morbidity and mortality during therapy. Published literature has documented that children with ALL have a 10-fold higher risk of invasive pneumococcal disease (IPD) during treatment for their cancer, with the highest risk occurring during maintenance chemotherapy. Importantly, this risk likely persists beyond the period of therapy receipt. The Childhood Cancer Survivor Study (CCSS) reported that survivors of all cancer were 1.6 to 2.7 times more likely to be hospitalized for infection >5 years following the completion of therapy compared with age-matched and sex-matched individuals in the general population. While these data are compelling there is a paucity of data documenting the frequency of infections or type of infections that occur in the first year following completion of therapy in children and adolescents with ALL. As such, clinicians do not have the necessary information to discuss infection risk with parents and their patients in this post-therapy period.

Additionally, there are limited data regarding the retention of seroprevalence for vaccine preventable infections during this post chemotherapy period. Significant interest exists in revaccinating children and adolescents after completion of therapy for ALL, however, the

---

necessity of such an intervention has not been clearly defined. Studies completed to date document that some children have low antibody titers to vaccine antigens immediately following treatment with therapy. However, these studies did not consider the possibility that patients further removed from their therapy will have more robust immune function recovery inclusive of vaccine antigen specific immune response. It is necessary to assess longitudinal recovery of immune function post-ALL therapy to better inform the need for revaccination among these children.

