#### **3.2.2 Total Number of Study Sites/Total Number of Subjects Projected**

The study will be conducted at seven investigative sites in the United States. Other sites may be added in the future. It is expected that approximately 115 subjects will be enrolled over the course of this study to produce 110 evaluable subjects. Evaluable patients will be defined as patients that are enrolled and at least one blood specimen collected.

For each of the 110 enrolled evaluable subjects in the ALL cohort, at the end of the follow-up period, three age- and sex-matched healthy control patients will be selected for comparison, to assemble a cohort of 330 total healthy control patients. The full cohort,

---

including both ALL patients and 3:1 matched controls, is anticipated to include 440 evaluable patients.

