### **3.3 Study Population**

#### **3.3.1 Inclusion Criteria for ALL Cohort**

1. Children, adolescents, and young adults ages 3 years to 31 years diagnosed with B or T ALL at age 12 months or older
2. Completed ALL chemotherapy within the past three months or will complete ALL chemotherapy in the upcoming three months (+/- 4 weeks)
  - **Blinatumomab sub-cohort (n = 20-25):** received ALL chemotherapy including the monoclonal antibody blinatumomab
3. Three years of age or older at time of enrollment.

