## 6 STATISTICAL CONSIDERATIONS

### 6.1 Primary Endpoint

The primary endpoint for Aim 1 of this study is to determine the incident infection rate in a cohort of subjects in the first year following completion of ALL therapy. Infections will include both clinical and/or microbiologically confirmed infections. All unique infections for a given subject will be captured and included in the final infection rate per person time estimate. Infections will also be reported in subsets of infections such as microbiologically confirmed (i.e., bacteremia, urinary tract infection or pneumonia with a positive sputum culture) or clinically defined infections. Additionally, a specific subset of infections to be described are sinopulmonary infections. This will include a medical encounter for otitis media, sinusitis, or pneumonia for which an antibiotic was prescribed. Infection events for matched healthy control patients will also be captured and used for comparison to the incident infection rate determined for the ALL participants.

The primary endpoint for Aim 2a is the proportion of patients with measles, varicella and pneumococcus antibodies at each study timepoint. Of note, pneumococcal serology results will include 23 serotypes: 1, 2, 3, 4, 5, 6B, 7F, 8, 9N, 9V, 10A, 11A, 12F, 14, 15B, 17F, 18C, 19A, 19F, 20, 22F, 23F, and 33F. Patients with detectable antibody to 50% or more of these serotypes will be considered to have seroprevalence for pneumococcus. This aim will also describe the total IgG levels at each time point at the individual and cohort level. Understanding the total IgG level will inform interpretation of vaccine-specific serology measures.

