### **7.3.3 Risk-Benefit Assessment**

This is a minimal risk study using data that will be collected prospectively from medical charts. The only potential risk would be loss of confidentiality. However, strict measures will be implemented to maintain confidentiality as detailed in this protocol. With the appropriate confidentiality measures in place, the risk to the subjects should be negligible. For the risk involved in obtaining blood collection, study teams will not obtain blood on a specific day if the clinical team determines that it will be detrimental to the study subject.

---

In view of the minimal risks to subjects participating in this study, and the considerable clinical and public health benefits which may ensue from it, the risk/benefit ratio is favorable.

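### Antibody status is planned only as three per-visit proportions; a within-patient gain/loss table and the number tested at each visit are needed before differences between visits can be read as recovery

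*Combined protocol and SAP*

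**What the plan says.** Section 6.1 defines the endpoint: "The primary endpoint for Aim 2a is the proportion of patients with measles, varicella and pneumococcus antibodies at each study timepoint". Section 6.3.3 analyses it as declared. Total IgG and seroprevalence "will be determined for the entire cohort and by demographics (e.g. age, race, gender) at each study follow-up time point", with further splits by completion of the primary vaccine series before chemotherapy and by blinatumomab.

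The stated purpose goes further. Section 1.2 argues: "It is necessary to assess longitudinal recovery of immune function post-ALL therapy to better inform the need for revaccination among these children". Section 1.1 likewise wants recovery documented, including immunity to particular vaccine-preventable organisms.

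On who contributes, section 3.2.2 states: "Evaluable patients will be defined as patients that are enrolled and at least one blood specimen collected". It expects that "approximately 115 subjects will be enrolled over the course of this study to produce 110 evaluable subjects". Nothing is said about how many of the 110 will have a sample at each visit.

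Within-patient description is planned elsewhere in Aim 2. Section 6.1 describes total IgG for individual patients as well as for the cohort, and section 6.3.3 plots lymphocyte subset trajectories. Neither is extended to antibody status.

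**The concern.** The same patients are to be bled at about 3, 6 and 12 months, and readers will compare the 3-month and 12-month proportions because the background invites them to. That comparison has two weaknesses.

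- **Changing membership.** If the patients tested at 12 months are not those tested at 3 months, the proportion can move although nobody's antibody status has changed.
- **Hidden turnover.** Even with complete sampling, two equal proportions can conceal losses balanced by gains. For a study meant to inform the need for revaccination, a stable cohort and one in which many patients lose antibody while others gain it are different findings.

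A third issue affects any comparison over time. Section 1.2 describes catch-up vaccination beginning 6 to 12 months after treatment. A rise by 12 months could therefore reflect vaccination during follow-up, yet section 6.3.3 splits only on the vaccine series completed before chemotherapy.

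**Working it through.** The documents give no precision or sample-size figure for seroprevalence (section 6.4 calls Aim 2 descriptive and omits power), so there is no figure of the plan's own to reproduce. The calculations below show scale only.

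**Inputs from the documents.** 110 evaluable patients out of 115 enrolled (section 3.2.2), so 5/115 = 4.3% are expected to give no specimen at all. This is not completeness by visit. The blinatumomab sub-cohort is 20 to 25 (section 3.1).

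**Assumed inputs.** The share m sampled at 3 but not at 12 months; the gap d in seroprevalence between those sampled and not sampled at 12 months; the seroprevalence itself; and the within-patient correlation rho.

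**1. Change produced by membership alone.** Suppose nobody changes status and everyone is sampled at 3 months. The 3-month proportion is m × s_missing + (1 − m) × s_seen, and the 12-month proportion is s_seen. The apparent change is the difference, m × (s_seen − s_missing) = m × d. In percentage points:

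| m | d = 10 | d = 20 | d = 30 |
|---|---|---|---|
| 5% | 0.5 | 1.0 | 1.5 |
| 10% | 1.0 | 2.0 | 3.0 |
| 20% | 2.0 | 4.0 | 6.0 |
| 30% | 3.0 | 6.0 | 9.0 |

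A simulation with 110 patients, m = 20%, and seroprevalence of 64% in those seen and 44% in those missing gave 3.99 points, against 4.0 by formula. The sign follows d, so the artefact can be a false rise or a false fall. It is zero when m = 0 or d = 0.

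**2. Hidden turnover.** With 60% seropositive at both visits in 110 patients, the share losing antibody can be anything from 0 to min(0.60, 0.40) = 0.40, that is 0 to 44 patients, offset by equal gains. The two proportions cannot show which.

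**3. Precision of the change.** With v = p(1 − p), the 95% half-width is 1.96 × sqrt((v3 + v12 − 2 × rho × sqrt(v3 × v12))/n). For 60% at both visits, v = 0.24:

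| n with both samples | rho = 0 (pairing ignored) | 0.3 | 0.5 | 0.7 |
|---|---|---|---|---|
| 110 | ±12.9 | ±10.8 | ±9.2 | ±7.1 |
| 88 (80% of 110) | ±14.5 | ±12.1 | ±10.2 | ±7.9 |

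At rho = 0.5 the paired interval is 1 − 9.2/12.9 = 29% narrower. The rho = 0 column is what a reader would get by differencing two published proportions as if they came from independent samples.

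**4. Small subgroups.** With 20 to 25 blinatumomab patients, one patient is 1/25 to 1/20, or 4 to 5 points, so a few missing draws could look like a trend.

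**The case against.** The strongest reply is that the plan analyses exactly what it declares. Section 2.2 sets out to describe seroprevalence at three times, section 6.1 makes the per-visit proportion the endpoint, and Figure 2 labels outcome 2a as status while reserving the recovery timeline for outcome 2b. This stands. A reader might infer that the planned proportions are wrong, or that change is the declared Aim 2a question; the documents support neither. What remains is that sections 1.1 and 1.2 also seek recovery over time, and the proportions alone cannot show it.

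A reader might also infer that sicker patients will be missing. Section 7.3.3 says only that "study teams will not obtain blood on a specific day if the clinical team determines" that it would harm the participant. That bars a draw on one day. Visits are approximately timed and tied to routine oncology appointments (section 3.2.1), so the draw could be deferred. Health-related missingness is possible but not shown. Section 6.3.3 refers to the entire cohort, so a shifting denominator is itself inferred from the one-specimen rule and the absence of a missing-sample rule. Entry up to about three months after therapy (section 3.3.1) is another route to a missed early draw, but its frequency is unknown.

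Finally, a reader might infer that the plan commits to an inefficient unpaired comparison. It specifies no test or interval for change at all, so the wider intervals above are not a property of the plan.

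The descriptive label does not remove the point. It explains the lack of a power calculation, but a descriptive comparison over time is still affected by who is in it, and a gain/loss table is itself descriptive.

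**Conclusion.** The point holds as a gap in the analysis plan, not as an error in the declared endpoint. For antibody status there is no within-patient summary, no visit denominator and no rule for missing specimens, so differences between the three proportions cannot be attributed to recovery. The gap does not extend in the same way to total IgG or lymphocyte subsets, for which patient-level description is already planned.

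No magnitude can be established. The range of about 0.5 to 9 points rests wholly on the assumed values of m and d, and the gain in precision on an assumed rho. The turnover result (0 to 44 of 110) needs no missing data, only the illustrative 60% at both visits. The change is worth making because the repeated samples are already planned and the addition costs almost nothing.

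**What to change.** In section 6.3.3:

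1. Keep the per-visit proportions. Report the number tested at each visit and the reasons for missing samples.
2. For each pathogen, cross-tabulate status within patients (kept, gained, lost, never) from 3 to 6 and from 3 to 12 months, with a paired 95% confidence interval for the change in patients who gave both samples. Say that this result describes those patients.
3. Show these tables by whether a relevant vaccine was given between the draws, so that revaccination is not read as recovery. Section 5.1.1 already lists vaccination records, but section 4.2.1 ties obtaining them to the baseline visit; state that abstraction runs to the 12-month draw.
4. As a supportive analysis, fit a marginal repeated-measures model to all samples with visit as a factor: GEE, or a mixed logistic model with its results converted to cohort proportions, since its coefficients are otherwise subject-specific. State the missing-data assumption. Unweighted GEE generally needs a stronger one than a likelihood-based mixed model.

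The cost is a paragraph of wording and a little more analysis. No further blood samples are needed.
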